4.7 ASSUMPTION CHECKING

All assumptions relating to the GLM models will be checked and evaluated whether appropriate to use with the data. Table 1 contains details of the assumptions associated with a GLM model and the methods to be used to assess these assumptions.

Assumption	Checking		
Generalised Linear mixed mod	el		
Linearity - the relationship between the independent and	scatter plots of the model		
dependent variables to be linear	residuals vs predictor		
Residuals/errors are independent - Little or no autocorrelation	n Scatter plot		
in the data. (residuals should be independent from each other)	er) Durbin-Watson test		
Residuals/Errors are normally distributed Q-Q-Plot			
Residuals/Errors have constant variance - There should be no	Scatter plot of standardized		
homoscedasticity of error terms	residuals versus predicted values		
No or little multi-collinearity - (independent variables should	inspection of correlation		
not be highly correlated with each other)	coefficients and Tolerance/VIF		
	values		

Outliers or unusual values will be assessed by running Grubbs (1969) test for outliers and visually inspecting a boxplot. No outliers will be discarded if they are within plausible range. Primary analysis will be conducted keeping the outliers in the dataset and if necessary, sensitivity analysis will be conducted by removing the outliers and evaluating any effects on the results and conclusions of analysis. Any outliers removed will be fully reported.

The distribution of the data will be checked and based on this a decision will be made as to whether a transformation should be applied and if so, which transformation should be used. If transformation is required, the distribution of the transformed data will be checked. Analysis will be reported on the original scale, transforming variables back. If a transformation is inappropriate, then nonparametric analysis methods will be considered.

4.8 ANALYSIS SETS

All primary analysis will be using modified ITT analysis (mITT), in which all randomised participants will be included who have taken at least one dose of trial medication.

For participants that were randomised but did not take any trial medication, they will be included in summary descriptive statistics only as they are not part of the mITT dataset (see figure 1).

A per protocol analysis set will also be used. This will consist of participants who took trial medication, at least until the first follow-up at 3 months. i.e. all those in the mITT set who withdrew from trial medication prior to their 3 month follow up are removed in addition to the participants randomised that didn't take trial medication at all.

5. DATA

All data will be handled in accordance with General Data Protection Regulation (GDPR, 2018). The Case Report Forms (CRFs) will not bear the subject's name or other personal identifiable data.

All electronic databases will use a patient identification number rather than the patient's name. Hard copies of data sheets linking the patient identification number to the person's contact details will be kept securely in a locked filing cabinet in a locked office and will only be accessible to a small number of people who are involved in the study. The database will be stored on a network drive at University of Bangor, which is backed-up daily.

Data monitoring will be carried out according to the trial-specific monitoring plan. At the end of the trial, data monitoring and cleaning will be completed and the database "locked" so that no further data entry is possible. At this point the data will extracted by the trial statistician along with the randomisation list stating whether participants were allocated to Arm A or B. The data will be analysed without knowledge of which arm relates to the active trial medication. Any subsequent 'unblind analysis' will be carried out once all blinded analysis is complete, reported to the study team and the Trial Statistician has been unblinded officially in accordance with NWORTH SOP.

5.1 TIME POINTS OF OUTCOMES MEASURES

Table 2 below details a list of the outcome measures being collected in the study and at which time points.

Assessments	Screening	Baseline	3-	6-	12 and 18-	Analysis
			month	month	month	
Structured Clinical Interview for Axis II Personality Disorders (SCID-II)	Х	-	-	-	-	Screening tool only - not being presented or analysed
Psychosis Screening Questionnaire	Х	-	-	-	-	Screening tool only - not being presented or analysed
International Personality Disorder Examination (IPDE)	Х	-	-	-	-	Screening tool only - being presented descriptively but not being analysed
Standardised Assessment of Severity of Personality Disorder (SASPD)	-	Х	-	Х	-	GLM analysis at 6 months
Zanarini rating scale for Borderline Personality Disorder (ZAN-BPD)	-	Х	Х	*Х	-	GLM analysis at 3 and 6 months
Brief Psychiatric Rating Scale (BPRS)	-	Х	Х	Х	-	GLM analysis at 3 and 6 months
Acts of Deliberate Self Harm Inventory	-	Х	Х	х	-	To be presented descriptively (count data) at each time point
Modified Overt-Aggression Scale (MOAS)	-	Х	Х	Х	-	GLM analysis at 3 and 6 months
EuroQoL EQ-5D 3 level	-	Х	Х	Х	-	For health economic analysis (being conducted as separate analysis)
The Antipsychotic Non-Neurological Side Effects Scale (ANNSERS)	-	Х	Х	Х	-	GLM analysis at 3 and 6 months
The Extrapyramidal Side Effects Scale	-	Х	Х	Х		GLM analysis at 3 and 6 months
Brief Adherence Rating Scale (BARS)	-		Х	Х	-	T-test at 3 and 6 months
Adult Service Use Schedule (ADSUS) Use of inpatient and community mental health services	-	Х	Х	Х	Х	For health economic analysis (being conducted as separate analysis)
Trial Arm allocation guess				Х		Independent variable for sensitivity analysis - not being used as an outcome measure.

*Primary outcome is Zan-BPD at 6 months.

5.2 DEFINITIONS AND CALCULATIONS OF OUTCOME MEASURES

The below list indicates the primary and secondary outcomes for the study.

Primary outcome

1. The primary outcome is total score on the Zanarini rating scale for Borderline Personality Disord er (ZAN-BPD) at six months.

Secondary outcomes

- 2. Total score on the Zanarini rating scale for Borderline Personality Disorder at three months.
- 3. General mental health using the Brief Psychiatric Rating Scale (BPRS) at three and six months.
- 4. Incidence and severity of suicidal behaviour using the Acts of Deliberate Self-Harm Inventory.
- 5. Level of aggressive behaviour using the Modified Overt Aggression Scale
- 6. Health related quality of life using the EQ-5D-5L.
- Side effects of medication using the Antipsychotic Non-Neurological Side Effects Scale (ANNSERS) and motor and extrapyramidal side effects using the Extrapyramidal Side Effects Scale.
- 8. Incidence of withdrawal of trial medication due to adverse effects.
- 9. Medication adherence at three and six months using the Brief Adherence Rating Scale.
- 10. Resource use collected using a modified version of the Adult Service Use Schedule and by examining clinical records at six, 12 and 18 months, This will include detailed information about length of inpatient treatment and type of ward (high, medium, low secure, Psychiatric Intensive Care, general adult etc.), contacts with community mental health services and emergency medical services, and the type and dose of psychotropic medication that people are prescribed.

For each measure, its associated analysis to be conducted is listed in table 2. Appendix 1 contains details and definitions of scoring these measures where applicable.

As detailed in the table, the SCID-II, Psychosis screening questionnaire and the IPDE are measures all used for screening and will not analysed. The IPDE will be used to describe the personality profile of the participants. The EQ-5D-3L and ADSUS are being collected for health economic analysis, which will be analysed and reported separately and summarised in a separate health economics analysis plan (HEAP). Additionally, physical health measures for participants are collected on a weekly basis as part

of physical and safety monitoring, these measures will not be summarised or presented as part of the analysis covered in this SAP, we will report on adverse events (see section 5.3 below).

5.3 SAFETY DATA

Safety data, covering the number of events and number of subjects affected split by treatment arm and categorised by event type (I.e. AE, AR, UAR, SAE, SAR, SUSAR) will be presented. Frequencies of system organ class (MEDDRAA code) will also be presented split by treatment arm.

Patients will be categorised based on whether they had an event or not (for each type) and this data will be summarised overall and by group. If appropriate (i.e. enough representation of yes/no) chi square test will be run on these and allocation group.

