6.5 CONSORT ANALYSIS

The patient flow information, shown in section 3.3 as advised by CONSORT reporting standards (Schulz et al., 2010), will be completed with values relating to participants numbers. Data will be presented on screening, eligibility, recruitment, treatment discontinuation, study withdrawals and lost to follow up, presented for the entire study and split by recruitment site. Where possible, reasons for ineligibility, non-recruitment, treatment discontinuation and withdrawal will be reported. From these data related eligibility, recruitment and retention rates will be calculated and presented.

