6.6 DESCRIPTIVE STATISTICS

Descriptive statistics of the data will be presented in the final analysis report. This will include randomisation figures, demographics, other data characteristics of the outcome measures and data completeness levels. All will be presented overall and split by allocation group.

Figures will be presented for the Randomisation data by each stratification variable;

- Allocation group
- Centre

- Gender (Sex at birth)
- Type of ward

The following demographics and data characteristics will be presented;

- Ethnicity
- Gender (self-identified)
- Age
- ICD-10 codes current admission and previous admission
- IPDE scores

Descriptive statistics of the primary outcome measures will be produced, these will be presented overall and split by allocation group. Additionally, the primary outcome descriptive statistics at baseline will be split by ward type. Furthermore, 3 and 6 months by trial arm allocation perception, see section 6.10 for more details. Descriptive statistics of the secondary outcome variables as listed in table 2will also be presented (overall and split by group).

For all statistics, continuous variables will be reported with mean values, standard deviations and ranges. Categorical variables will be presented with counts and percentages. If data are not normally distributed, then medians and interquartile ranges will be reported.

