6.10 SENSITIVITY ANALYSES OR MODEL TESTING

Some exploratory sensitivity analysis will be conducted; however, this will be limited due to the small sample. Sensitivity analysis results and interpretation, as with the main analysis, should be treated with caution due to the small sample and lack of statistical power.

Sensitivity analysis may be required around any assumptions made for the primary analysis (e.g. outliers, data distributions) but only if necessary. Complete case analysis will be conducted on the primary and secondary data models to check the impacts of multiple imputation on the results at 6 and 12 months.

As indicated, primary and secondary outcomes will firstly be analysed as a mITT analysis. Sensitivity analysis will be carried out on a per protocol analysis (participants who took trial medication, at least until the first follow-up at 3 months) at 6 and 12 months on the primary outcome.

A sensitivity analysis around treatment arm allocation perception will be conducted. This separates into two parts (blinded analysis and unblinded analysis). Firstly, blinded, we will look at the 'view of allocation' i.e. did their view of whether they had placebo or active impact on Zan-BPD scores. For both the assessor and patient, ZAN-PBD scores, will be summarised descriptively, split by 'view of allocation arm' (regardless of what they actually had). For participants the primary outcome model will be run with this variable included to assess any impacts on the scores. In addition, patients view of their allocation and whether they discontinued from study medication, and if so at what time point, will be presented descriptively. This will be conducted on the mITT data set and the per protocol set.

Subsequently, following all blinded analysis being conducted, statistics of numbers of patients and assessors that correctly guessed their allocation will be presented, and in which direction (i.e. thought they were on placebo and were right or wrong or thought they were on active and were right or wrong).

Finally, a sensitivity analysis that adjusts any difference seen between treatment arms according to whether the participant reported 'lethargy/lassitude', as measured by the ANNSERS, will be conducted. This will be carried out by including the ANNSERS item for 'lethargy/lassitude' as an independent variable in the analysis model on the ZAN-BPD at 3 and 6 months. This will be on both the mITT and per protocol analysis sets.

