6.13 SAFETY AND TOLERABILITY ANALYSIS

Safety and tolerability analysis is not applicable for the CALMED Trial and will not be conducted as part of the study analysis. Adverse event data for the trial will be summarised (see section 5.3) but not in relation to safety and tolerability analyses.

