APPENDIX 1 – OUTCOME MEASURES SUMMARY

Purpose	Scoring	Item Coding	Subscales	Direction	Missing value rules	Thresholds
Acts of Deliberate Self Harm Inv	entory					
Assess deliberate self-harm	Measure used in study is different from published measure. Scoring not applicable, descriptive statistics of events will be summarised for measure, like adverse event data presentation.	n/a	n/a	n/a	n/a	n/a
The Antipsychotic Non-Neurolog	gical Side Effects Scale (ANNSERS)					
Comprehensive measure for rating non-neurological adverse drug reactions (ADRs) to antipsychotic	 43-item scale. No. of items for each side effect severity 'class' (mild, moderate, severe) is summed. (Note item 44 is not included in total) Total score is calculated by multiplying the number of items tallied for each severity class by the item code for that class. Total score ranges from 0 - 129 Example: None – 30, Mild total – 3, Moderate, total – 9, Severe – 1 Total (0x30) + (3x1) + (9x2) + (1x3) = 21 	None – 0 Mild – 1 Moderate – 2 Severe - 3	none	Higher scores indicate more severe side effects i.e. "Higher worse"	None found	None found
Brief Adherence Rating Scale (B	•					
	ny, A. John Rush (2008). The Brief Adherence Ratin ive disorder, Schizophrenia Research, Volume 100,					herence of outpatients
Assess the oral antipsychotic medication adherence	4-item scale. 3 questions and one visual analogue scale (VAS) 1 rating (0-100%). The VAS rating serves as the final adherence determination, therefore, total	n/a	None	Higher scores indicate better adherence i.e. "Higher better"	None found	None found
	score ranges from 0-100			i.e. nigher better		

Brief Psychiatric Rating Scale (BPRS)

1 Sychiatry Rescarch, 210(2), 020 05	5. https://doi.org/10.1010/j.psychies.2015.07.001		1			
measure patient's	24-item scale, each rated on a 7-point	0 = not assessed	None found	Higher scores	None found	None found
psychopathology	Likert scale (see item coding).	(Missing) [not counted in		indicate more		
		final score].		severe symptoms		
	Total score is calculated by summing					
	items, hence ranges from 24 – 168.	1 = not present, 2 = very		i.e. "Higher worse"		
		mild, 3 = mild, 4 =				
		moderate, 5 =				

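### The planned by-arm safety outputs stop at system organ class and one ANNSERS total, so they cannot show which non-neurological side effect differs between clozapine and placebo

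*SAP*

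**What the plan says.** Section 5.3 gives adverse events by arm as numbers of events and subjects within regulatory type (AE, AR, UAR, SAE, SAR, SUSAR). It adds a yes/no indicator per type, with a chi-square test if the data allow. The only finer level is the organ class: "Frequencies of system organ class (MEDDRAA code) will also be presented split by treatment arm".

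For ANNSERS, Appendix 1 lists no subscales and defines a single score: "Total score is calculated by multiplying the number of items tallied for each severity class by the item code for that class". Table 2 and 6.8 model that score at 3 and 6 months. Section 6.6 adds descriptive statistics by group for the Table 2 variables, which for ANNSERS means the same total.

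One ANNSERS item is used alone. Section 6.10 adjusts for lethargy by "including the ANNSERS item for 'lethargy/lassitude' as an independent variable in the analysis model on the ZAN-BPD at 3 and 6 months". No by-arm count of it is planned.

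Other sections do not go finer. Of the weekly physical health measures, 5.2 says "these measures will not be summarised or presented as part of the analysis covered in this SAP". Section 6.13 says "Adverse event data for the trial will be summarised (see section 5.3) but not in relation to safety and tolerability analyses". Self-harm is the exception, with its own entry in Table 2: "To be presented descriptively (count data) at each time point".

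**The concern.** Section 3.1 gives the unknown risks and benefits of clozapine in these patients as the reason for the trial, and 5.2 lists side effects of medication among the secondary outcomes. With 29 randomised patients, the SAP says in sections 2 and 4.3 that it cannot give conclusive evidence. A plain description of what patients experienced in each arm is therefore among the more useful things the trial can still report.

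The plan does not leave the level of that description open. It fixes it at organ class for adverse events and at one summed score for ANNSERS. A clinician reading the report would learn that one arm had more events in a body system, or a higher total burden, without learning what the side effect was. The item and event data are collected, so the loss lies in reporting only.

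**Working it through.** The point concerns which outputs are planned, so the main check compares the sections.

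**1. Routes by which a by-arm result for a single non-neurological side effect could appear**

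- 5.3, regulatory type: classifies seriousness, causality and expectedness, and does not name the event.
- 5.3, system organ class: narrows to a body system, but one class pools several distinct events.
- Table 2, 6.8 and Appendix 1, ANNSERS: one total per patient and visit.
- 6.6, descriptive statistics by group: applies to the Table 2 variable, hence the total.
- 4.6, item level: completion rates only.
- 5.2, weekly physical measures: excluded.
- 5.2, withdrawal of medication due to adverse effects: an incidence, with no effect named.
- 6.10, lethargy/lassitude: a covariate in the ZAN-BPD model, with no by-arm tabulation.
- 6.13: refers back to 5.3.

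None reaches a named non-neurological side effect by arm. Self-harm counts are a separate output. The Extrapyramidal Side Effects Scale is also a single sum, but it is neurological and outside this point.

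**2. What the ANNSERS total can and cannot show**

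Inputs from Appendix 1: 43 items, codes 0 to 3. Maximum = 43 × 3 = 129, which reproduces the stated range.

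Take five items, A to E (illustration):

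- Patient 1: A = 3, B = 2, C = 1, others 0. Total = 3 + 2 + 1 = 6.
- Patient 2: C = 1, D = 3, E = 2, others 0. Total = 1 + 3 + 2 = 6.

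If every patient in one arm had the first profile and every patient in the other had the second, the difference in mean totals would be 6 − 6 = 0, although the arms differ on four of the five items. Conversely, a non-zero difference does not say which item produced it.

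**3. Size of a table that would show it**

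Baseline presence: 43 items × 2 arms = 86 counts. Newly present or worsened at 3 and 6 months: 43 × 2 arms × 2 visits = 172. Total = 86 + 172 = 258 counts at most, before items that never occur are dropped.

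**4. How such a table would behave with no true difference**

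Assumptions, none given in the SAP: all 29 patients observed, split 14/15; items independent; the same prevalence p in both arms; one visit. Let q be the probability that the two observed proportions on one item differ by at least 30 percentage points, from two binomials with n = 14 and n = 15. The probability of at least one such gap is 1 − (1 − q)^43.

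| p | q | 1 − (1 − q)^43 |
|---|---|---|
| 10% | 0.0063 | 24% |
| 20% | 0.0388 | 82% |
| 30% | 0.0854 | 98% |

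Correlated items or missing visits would change these figures. Large single-item gaps should still be expected by chance, and the table must say so.

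**The case against.** The strongest reply is that nothing in the SAP is wrong or contradictory here. It fixes a recognised level of adverse-event reporting, scores ANNSERS by a stated rule and does not forbid finer tables. On that view this is a request for table-shell detail. Part of this stands: no estimate, test, population or conclusion changes, so the point is minor. It does not remove the point, because the SAP states a reporting level and a better one is available from the same data.

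A second reply is that an item table on 29 patients will mislead. The chance figures above bear this out, and they are the reason for omitting p-values and adding an explicit caution. They are not a reason to publish only aggregates.

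Three stronger readings are tempting and are not supported.

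- A reader might infer that the lethargy adjustment in 6.10 cannot be interpreted because its coefficient is not promised. The fitted model produces that coefficient, and 4.3 promises 95% confidence intervals with any p-value or effect, which arguably covers it.
- A reader might infer that discontinuation is never shown by arm, since 6.5 speaks of "treatment discontinuation, study withdrawals and lost to follow up, presented for the entire study and split by recruitment site". But withdrawal of medication due to adverse effects is a listed secondary outcome, and 6.5 also relies on the flow diagram in 3.3, which could not be seen. The documents do not settle this.
- A reader might try to size the loss by passing a lopsided hypothetical side effect through the ANNSERS model. That needs an ANNSERS standard deviation, which the SAP does not give. It also ignores that the same effect, if recorded as an adverse event, would appear in the organ-class table.

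**Conclusion.** The point holds as a minor, cheap improvement. As written, the by-arm outputs can show that a body system or the total ANNSERS burden differs, but cannot identify which non-neurological side effect does. This rests on the SAP text alone. Individual listings may exist under the protocol or other documents that are not shown, but the SAP makes no by-arm commitment below organ class or ANNSERS total.

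It would be wrong to conclude that the safety analysis is invalid or that safety data are withheld. By-arm events, subjects, organ classes and ANNSERS totals are all planned. No numerical size is claimed for the information lost. The chance-gap percentages depend on assumed prevalences, independence of items and a 14/15 split, and they serve only to show how the added table must be labelled.

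**What to change.** - **5.3:** tabulate adverse events by MedDRA preferred term within system organ class, as subjects and events per arm.
- **5.3 or 6.8:** keep the ANNSERS total model unchanged. Add one compact by-arm table of the ANNSERS items that occurred in at least one patient, including lethargy/lassitude, from observed values: number present at baseline, and number newly present or worsened at 3 and at 6 months.
- **Labelling:** mark the item table as descriptive, give no p-values, and state that with 43 items and 29 patients sizeable gaps between arms on single items are expected by chance.
- **Timing:** produce both tables after the blinded analysis, because a recognisable side-effect pattern could reveal which arm is active. Sections 5 and 5.4 already provide for an unblinded stage.

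The cost is a few lines of SAP text and some table programming on data already collected. The downside is longer, sparse tables. The sample size, primary analysis and planned models do not change.
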